3.0 STUDY DESIGN

3.1 Description

The proposed project falls into the scope of what has been termed a pragmatic or practical clinical trial [109-111]. This means that the hypothesis and study design have been developed specifically to answer questions faced by policy makers as they seek to develop new and effective population health management approaches. The first goal is to develop a CDSS that has undergone preliminary assessment of its clinical usefulness by knowledge opinion leaders as well as practical field-testing of its utility and dependability in practice settings. Following this, a rigorous analytical assessment of efficacy will be undertaken.

Specifically, IMPACT-AF will include a prospective, randomized, unblinded cluster design clinical trial, proposed to take place within Nova Scotia over the time period of 2014-2018, that will investigate whether a Clinical Decision Support System (CDSS) improves the clinical outcomes of patients with AF. Primary care providers (n=200) will be randomized to usual care versus use of the CDSS in a 1:1 fashion, at the level of the clinic practice. In order to facilitate the study, primary care providers will be required to have high speed internet access. The study will follow patients over a minimum of 12 months after enrolment.

Patients Included in the Analysis:

1. Age \geq 18 years
2. Electrocardiographically confirmed atrial fibrillation or documentation of past diagnosis or management of AF in the patient's medical record
3. Able to provide informed consent in English
4. Resident of Nova Scotia

Exclusion Criteria:

1. Patients unable to provide informed consent
2. Patients who have a terminal illness and are not expected to be alive at the end of follow up.

3.2 Study Flow:

See Figure 5 for a Summary of Study Flow.

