3.6 Sources of Bias

In cluster-randomized trials, there are important sources of bias to consider: recruitment bias, baseline imbalance and loss of clusters [122]. Recruitment bias should be limited as all patients in each PCP practice will be included, thereby minimizing bias in types of AF patients. Baseline imbalance is unlikely to be an issue as there are a large number of clusters in this study. Loss of clusters is possible but unlikely since there is little migration of PCPs from Nova Scotia; thus, loss of an entire cluster over the period of follow-up is improbable.

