3.7 Study Procedures

3.7.1 Randomization

Primary care centres will obtain their randomized assignment (intervention versus control) at the time of recruitment. (See Section 4.0 for Study Recruitment Procedures.) Randomization will be stratified by whether the PCP is urban or rural. Urban is defined as a population $\geq 10,000$, while rural is defined as $< 10,000$ population [123].

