3.7.2 Treatment Period and Follow-up

The study will recruit PCPs until the goal of 200 is achieved, then follow patients for a minimum of 12 months. The intervention will be set up with appropriate training in the PCP practice prior to testing the intervention. There are no specific study visits for this trial; however, any unplanned PCP visits, emergency department visits and hospitalizations will be examined for important data (See Table 2).

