3.8 Sample Size

The primary objective of the proposed study is a composite of unplanned cardiovascular hospitalizations in AF patients and any AF-related emergency department visits. The sample size calculation is based on the test of the null hypothesis that the percentages of patients with cardiovascular hospitalizations in the two populations (CDSS and usual care) are equal. The primary measure of effect is the difference in proportions of patients with composite of any AF-related emergency department visit or unplanned CV hospitalization over 12 months. The criterion for significance (alpha) has been set at 0.05. With the proposed sample size of 1075 primary care patients (537 per intervention/control arm, assuming a 1:1 allocation ratio), the study will have power of 80% to yield a statistically significant absolute difference of 10% (or 20 [RRR] relative risk reduction) between the two percentages of patients with composite of any AF-related emergency department visit or unplanned CV hospitalization in the control and intervention groups, assuming 50% annual rate of CVD hospitalizations for the control group. This sample size was adjusted for a potential clustering of patient outcomes within a physician, by assuming an intra-physician correlation coefficient (ICC) of 0.05 with an average cluster size of 9 patients/physician. The ICC is based on studies done in the primary care sector reporting this magnitude of ICC. This extent of reduction was felt to represent a minimal clinically important achievement by a consensus of study investigators and has been an endpoint target in other studies in AF populations of similar design [127-129].

Table 3 provides a summary of the sample size calculation for different values of the baseline control rate (50%, 58%), RRR (15%, 20%, 25%, 30%), intra-class correlation coefficient [ICC] (0.05, 0.10) and average cluster size (m) (9,12,15). The primary measure of effect is the difference in the proportions or percentages of patients with cardiovascular hospitalizations and AF-related emergency room visits across study arms over an active study period of 12 months. The criterion for significance (alpha) has been set at 0.05. The test is 2-tailed, which means that an effect in either direction will be interpreted. The statistical power is set at 80%.

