The above computation assumes a binomial distribution for the number of patients with cardiovascular hospitalizations and AF-related ED visits, a baseline control rate of about 50% and hypothesized RRR of 20%. We also adjusted the sample size for a potential clustering of patient responses within a practice group, varying the intra-class correlation coefficient (ICC)—which measures the degree of clustering – from 9-15 (see Table 3). Therefore, the required sample size of 1075 patients corresponds to an ICC of 0.05 and average cluster size of m= 9.

P0= the proportion of patients in the control group

MCID=minimal clinically important difference/improvement

P1=proportion in the intervention group

n=Total unadjusted sample size

ICC=intra-cluster/practice correlation coefficient

m=average cluster size

VIF=1+(m-1)ICC=variance inflation factor

n_adj=n*VIF=Total adjusted sample size (adjusted for clustering)

RRR = relative risk reduction

The calculations are based on

CONFIDENTIAL

Control rate of 50% and 58% based on the NS data
RRR varying from 15% to 30%
Average cluster sizes (m) of 20, 25 and 30
ICC values of 0.05 and 0.10
Alpha = 0.05 Beta = 0.20

Table 3. Sample size Calculation

CONFIDENTIAL

P0	RRR	MCID	P1	n	ICC	m	VIF	n_adj	k
0.58	0.3	0.174	0.406	251.0602299	0.05	9	1.4	351.4843218	39.05381354
0.58	0.3	0.174	0.406	251.0602299	0.05	12	1.55	389.1433563	32.42861303
0.58	0.3	0.174	0.406	251.0602299	0.05	15	1.7	426.8023908	28.45349272
0.58	0.25	0.145	0.435	364.9655172	0.05	9	1.4	510.9517241	56.77241379
0.58	0.25	0.145	0.435	364.9655172	0.05	12	1.55	565.6965517	47.14137931
0.58	0.25	0.145	0.435	364.9655172	0.05	15	1.7	620.4413793	41.36275862
0.58	0.2	0.116	0.464	573.6717241	0.05	9	1.4	803.1404138	89.23782375
0.58	0.2	0.116	0.464	573.6717241	0.05	12	1.55	889.1911724	74.09926437
0.58	0.2	0.116	0.464	573.6717241	0.05	15	1.7	975.241931	65.01612874
0.58	0.15	0.087	0.493	1022.444138	0.05	9	1.4	1431.421793	159.0468659
0.58	0.15	0.087	0.493	1022.444138	0.05	12	1.55	1584.788414	132.0657011
0.58	0.15	0.087	0.493	1022.444138	0.05	15	1.7	1738.155034	115.8770023
0.58	0.3	0.174	0.406	251.0602299	0.1	9	1.8	451.9084138	50.21204598
0.58	0.3	0.174	0.406	251.0602299	0.1	12	2.1	527.2264828	43.93554023
0.58	0.3	0.174	0.406	251.0602299	0.1	15	2.4	602.5445517	40.16963678
0.58	0.25	0.145	0.435	364.9655172	0.1	9	1.8	656.937931	72.99310345
0.58	0.25	0.145	0.435	364.9655172	0.1	12	2.1	766.4275862	63.86896552
0.58	0.25	0.145	0.435	364.9655172	0.1	15	2.4	875.9172414	58.39448276

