4.0 Study Population

4.1 Recruitment of Clinics and Practitioners Managing AF Patients

IMPACT-AF will seek participation from a wide variety of primary care providers managing AF patients within Nova Scotia. All patients with a prior or new electrocardiographically confirmed diagnosis of AF during the study period will be eligible for inclusion as part of the study.

Inclusion Criteria: Any licensed medical provider of community-based adult patients with a minimum of 15 diagnosed AF patients enrolled in the study from their practice will be eligible to participate. To avoid bias based on technological availability or proficiency, all eligible providers are required to have access to high-speed internet access in their office for the duration of this study. As well, participating providers must sign a site agreement which outline the following terms:

- Agree to participate for the duration of the study;
- Notify the research team if your practice:
 - Is located in an urban (population $\geq 10,000$) or rural (population $< 10,000$) setting; and,
 - Operates as a collaborative practice (i.e., shares in the care of patients with at least one other health care provider);
- Attend and participate in investigator meetings;
- Identify all eligible patients in your practice who meet the study inclusion criteria;
- Invite all eligible participants to join in the study (either in person or via mail outs);
- Perform informed consent discussions with eligible participants who visit your practice for routine care;
- Accept randomization into either the control or intervention group;
- Agree to store informed consent forms and completed patient questionnaires in locked filing cabinets in an access-controlled location within your practice (after faxing a copy to the study office);
- Agree to be trained on and use the web-based decision support tool, if assigned to the intervention group;
- Allow the study team access to medical records for consented study participants at baseline and follow-up;
- Facilitate the distribution of patient questionnaires (all materials supplied by the research team);

CONFIDENTIAL

- Notify the Privacy Officer at HITS-NS that the study team is to be granted access to data for all patients who consent to study inclusion and provide copies of patient signed consent forms as requested.
- Report any problems that you experience related to your participation in the study.

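### The 80% power for 1075 patients rests on 9 patients per cluster, a figure not reconciled with the practice as randomized unit or with the 15-patient minimum in 4.1

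*Protocol*

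**What the plan says.** Protocol 3.8 sets 1075 patients (537 per arm) for 80% power, two-sided alpha 0.05, 50% versus 40%. The clustering allowance is made "by assuming an intra-physician correlation coefficient (ICC) of 0.05 with an average cluster size of 9 patients/physician". The following paragraphs of 3.8 describe the same allowance as being for "potential clustering of patient responses within a practice group". The legend to Table 3 labels the ICC as cluster/practice level, and 1075 is again tied to a cluster size of 9. The legend's assumptions then list "Average cluster sizes (m) of 20, 25 and 30", although Table 3 uses only 9, 12 and 15.

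On the randomized unit, Protocol 3.1 says that 200 providers "will be randomized to usual care versus use of the CDSS in a 1:1 fashion, at the level of the clinic practice". Protocol 3.9 names the practice as unit of randomization and clusters the GEE on practice. The SAP (Primary Outcome Analysis) also clusters on practice, but gives the unit of randomization as practice or physician, joined by a slash.

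On cluster size, Protocol 4.1 says that a provider with "a minimum of 15 diagnosed AF patients enrolled in the study from their practice will be eligible to participate". Protocol 4.2 estimates 20 to 30 diagnosed AF patients in an average family practice. Protocol 3.6 says that "all patients in each PCP practice will be included", though individual consent is required. On timing and numbers, 3.7.1 says "Primary care centres will obtain their randomized assignment (intervention versus control) at the time of recruitment", and 3.7.2 says "The study will recruit PCPs until the goal of 200 is achieved".

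**The concern.** The design effect 1 + (m − 1) × ICC must use the size of the cluster that is randomized. If practices enrol more than 9 patients on average and the total stays near 1075, the effective sample is smaller than 3.8 assumes. The entry rule in 4.1, read as written, puts every practice at 15 or more, so the average could not be 9.

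What is at stake is the reading of a neutral result. A trial reported as having 80% power to detect a 10-point difference supports a firmer negative conclusion than one with about 72%. The usual-care column of the SAP's Table 2 shell (N=543) fits a total near 1075, which is the setting in which larger practices cost power.

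**Working it through.** **Inputs.** From Protocol 3.8: two-sided alpha 0.05, 80% power, 50% versus 40%, 1:1 allocation, total 1075, ICC 0.05, m = 9. From the Table 3 legend: VIF = 1 + (m − 1) × ICC, with the ICC at practice level. From 3.1 and 3.7.2: 200 providers. From 4.1: minimum 15. Equal cluster sizes throughout, as in the plan.

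**Step 1: reproduce the plan.** Unadjusted total = 2 × (1.96 + 0.84)² × (0.5 × 0.5 + 0.4 × 0.6) / 0.1² = 768.32, as in Table 3. VIF at m = 9 is 1.40, and 768.32 × 1.40 = 1075.65. Power with 1075 is Φ(0.1 / √(0.49 × VIF / 537.5) − 1.96) = Φ(2.799 − 1.96) = 79.9%. The arithmetic of 3.8 is correct at m = 9.

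**Step 2: use the 4.1 minimum as the practice size.** VIF at m = 15 is 1.70. Required total = 768.32 × 1.70 = 1306.1, which is Table 3's own entry and 231 more than planned. Power with 1075 is Φ(2.540 − 1.96) = 71.9% (71.6% with a pooled variance).

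**Step 3: tie cluster size to 200 providers and 1075 patients.** Practices = 1075/m; providers per practice = 200m/1075.

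| Mean per practice | Practices | Providers per practice | VIF | Total for 80% | Power at 1075 |
|---|---|---|---|---|---|
| 5.4 | 200 | 1.0 | 1.22 | 936 | 85.1% |
| 9 | 119.4 | 1.7 | 1.40 | 1076 | 79.9% |
| 10.8 | 100 | 2.0 | 1.49 | 1143 | 77.5% |
| 12 | 89.6 | 2.2 | 1.55 | 1191 | 75.8% |
| 15 | 71.7 | 2.8 | 1.70 | 1306 | 71.9% |

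Table 3 gives 119.5 clusters at m = 9 because it divides 1075.648 by 9. If each provider were a cluster of 9, the total would be 200 × 9 = 1800, not 1075.

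**Step 4: let the ICC be a physician-level figure.** Section 3.8 also calls the 0.05 an intra-physician value. Assume 0.05 within a physician (1075/200 = 5.375 patients each) and a smaller correlation r between patients of different physicians in one practice. Then VIF = 1 + 4.375 × 0.05 + (15 − 5.375) × r at 15 per practice. The documents give no r, so a range is shown:

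| r | VIF | Power at 1075 |
|---|---|---|
| 0 | 1.219 | 85.1% |
| 0.0125 | 1.339 | 81.7% |
| 0.025 | 1.459 | 78.3% |
| 0.05 | 1.700 | 71.9% |

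**Step 5: cases with no loss.** If 200 single-provider practices each enrolled 15, the total would be 3000 and power 98.9%. At Table 3's other control rate (58%, 20% relative reduction), m = 15 needs 975 patients, and 1075 give 83.6%.

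**The case against.** The best defence is that 3.8 already states a practice-level figure: its second description of the adjustment and the Table 3 legend attach m = 9 to the practice, with 119.5 clusters. Spread over those, 200 providers make about 1.7 each, and 4.1 expects some practices to be collaborative. This stands. A reader might infer that the plan gives no practice average at all, and the documents do not support that. What is missing is agreement between that average and the rest of the text.

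Second, the 15 may mean diagnosed patients available. The rule decides who may take part, and centres are randomized when recruited, so a count of enrolled patients is awkward as an entry test. Nine enrolled out of 20 to 30 diagnosed is 30% to 45%, plausible given individual consent and the exclusions in 4.2. This also stands as a possible reading, but 4.1 says enrolled, so the sponsor must say which is meant.

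Third, the loss depends on applying 0.05 across the whole practice (Step 4). That stands and limits the size.

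Fourth, the analysis clusters on practice, so the test and interval allow for the actual clustering whatever 3.8 assumed. True, but the stated power is a separate claim and is not corrected by the analysis.

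A reader might also work out power at 20 to 30 per practice. The documents do not support treating that as the expected case: Table 3 never uses those sizes, and the 20 to 30 in 4.2 are diagnosed patients, not consented ones.

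**Conclusion.** The concern holds as an unreconciled input to a stated power. The calculation is reproducible at 9 per cluster, but 3.8 names two different clusters for that 9, and 4.1 as worded rules out 9 as a practice average. On the literal reading, with a total near 1075 and ICC 0.05 across the practice, power is about 72% and not 80%. That case implies about 2.8 providers per practice, which the documents do not state.

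A reader might conclude that the trial is underpowered. The documents do not establish that. If the 15 are patients identified, 80% can stand at 9 per practice. If most practices have one provider and share 1075 patients, power is about 85%. At 15 per practice with weaker correlation between physicians, it is about 78% to 85% for r between 0.025 and 0. What can be said is that the reader cannot tell from the text which of these applies. The figures concern the two-proportion comparison in 3.8; the SAP's primary effect measure is a hazard ratio.

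**What to change.** In Protocol 3.8:

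- Name the practice as the cluster for both the ICC and the cluster size.
- State the expected number of practices and the mean enrolled per practice, consistent with 200 providers, 1075 patients and the 4.1 minimum. For a mean of 9 this is about 120 practices of about 1.7 providers.
- Restate the power that 1075 patients give at that mean: 80% at 9, 77.5% at 10.8, 76% at 12, about 72% at 15, with ICC 0.05 for the practice.
- Delete the line listing cluster sizes of 20, 25 and 30.

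In Protocol 4.1, say whether the 15 are AF patients identified in the practice or enrolled from it.

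The cost is a few sentences. No patients are added and the analysis is unchanged. The only downside is that the stated power falls if the reconciled practice mean is above 9.

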The analysis and reporting of the trial results will follow the CONSORT Statement for cluster-randomization trials [129]. The baseline characteristics of the practices and patients will be reported by group as mean (standard deviation) or median (first quartile, third quartile) for continuous variables, depending on the distribution, and count (percent) for categorical variables. The analysis will follow the intention-to-treat (ITT) principle. The unit of randomization will be the practice. The unit of analysis will be the patient. We will use multiple imputation to handle missing data to enable ITT analysis. Multiple imputation is a Monte Carlo technique in which the missing values are replaced by $m > 1$ simulated versions, where 'm' is typically small. Each of the simulated complete datasets will be analyzed by standard methods, and the results will be combined to produce estimates and confidence intervals that incorporate missing data uncertainty [133]. We will use generalized estimating equations (GEE) – assuming exchangeable correlation structure for patients within the same practice, and adjusting for urban and rural practice types to analyse all outcomes [130]. Unlike ordinary regression techniques, GEE allows us to model the intra-practice correlation among patients within each practice. The results will be reported as the estimate of the effect, corresponding 95% confidence interval and associated p-values. All p-values will be reported to three decimal places with those less than 0.001 reported as $p < 0.001$. The criterion for statistical significance will be set a priori at $\alpha = 0.05$, and adjusted using the Bonferroni method for multiple secondary analyses. All analyses will be performed using SAS 9.4 (Cary, NC).

Sensitivity analyses: 1) There are several methods for analyzing cluster RCTs [131]. Therefore, we will perform sensitivity analyses using some of the commonly used patient-level methods such as random-intercept model and cluster-level (i.e. random- and fixed-effects meta-analytic) methods to assess the robustness of the results. 2) Given that the unit of randomization is the practice, there is a higher chance of potential imbalance of patient-level baseline characteristics. We will perform some sensitivity analysis to adjust for any potential imbalance.

HRQoL

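### The stated 80% power has no slack at nine patients per cluster, because section 3.8 assumes equal-sized clusters and every patient analysed; it should be restated from the actual practice sizes

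*Protocol*

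**What the plan says.** Protocol section 3.8 compares 50% with 40% over 12 months. The control rate is introduced as "assuming 50% annual rate of CVD hospitalizations for the control group". On error rates it says "The criterion for significance (alpha) has been set at 0.05" and "The test is 2-tailed, which means that an effect in either direction will be interpreted"; power is 80%. The unadjusted total is multiplied by one factor only, "VIF=1+(m-1)ICC=variance inflation factor", where m is the average cluster size (9, per physician) and the ICC is 0.05. The power claim begins "With the proposed sample size of 1075 primary care patients".

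Table 3 varies the control rate, the relative risk reduction, the ICC and the average m. It does not vary the spread of cluster size and has no allowance for loss. Section 3.9 makes the practice the unit of randomisation, specifies GEE with an exchangeable correlation within practice, and adds "We will use multiple imputation to handle missing data to enable ITT analysis". Section 3.6 judges the loss of a whole cluster improbable, without a figure. Among the terms that providers must accept, section 4.1 asks them to report whether the practice "Operates as a collaborative practice (i.e., shares in the care of patients with at least one other health care provider". The SAP does not revisit the sample size.

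**The concern.** A design effect built on the average cluster size alone understates the variance when sizes differ, and here they will differ. Whole practices are randomised, urban and rural, single-handed or shared, and each contributes whichever of its eligible patients consent. Separately, the enrolled total equals the calculated requirement, so it is implicitly assumed that every enrolled patient contributes an outcome. Multiple imputation carries the uncertainty from missing values into the confidence interval, but it does not in general restore information lost with missing outcomes.

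The 80% is therefore the top of the range at m = 9, yet section 3.8 presents it as the design value. A null result would be set against a power that the design probably does not have at that cluster size.

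**Working it through.** **Inputs from the documents** (Protocol 3.8): 50% vs 40%, two-sided alpha 0.05, power 80%, 1:1 allocation, ICC 0.05, m = 9, total 1075.

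**Assumed, because the documents give neither:** CV of cluster size 0.4 to 0.8; loss of outcome data 0% to 10%.

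**Step 1: reproduce the plan.**
- Unadjusted total: n = 2 × (1.96 + 0.84)² × (0.25 + 0.24) / 0.10² = 768.32.
- VIF = 1 + (9 − 1) × 0.05 = 1.40.
- 768.32 × 1.40 = 1075.648, which matches Table 3.
- Power = Φ(0.10 / √(0.49 × VIF / (N/2)) − 1.96). With N = 1075 and VIF = 1.40: 0.10 / √(0.49 × 1.40 / 537.5) = 2.799, and Φ(0.839) = 79.9%.

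**Step 2: unequal cluster sizes.** Two design effects (DE) are used.
- Size-weighted estimator (conservative here): DE = 1 + ((1 + CV²)m − 1) × ICC.
- Approximation for exchangeable GEE: DE = (1 + (m − 1) × ICC) / (1 − CV² × L(1 − L)), with L = m × ICC / (m × ICC + 1 − ICC).

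At m = 9, L = 0.45 / 1.40 = 0.321 and L(1 − L) = 0.218. For CV 0.6 the GEE value is 1.40 / (1 − 0.36 × 0.218) = 1.519, so power = Φ(0.10 / √(0.49 × 1.519 / 537.5) − 1.96) = Φ(0.727) = 76.6%. The size-weighted value is 1 + (1.36 × 9 − 1) × 0.05 = 1.562, which gives 75.5%.

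**Step 3: loss.** A loss fraction d reduces both the analysed total, to 1075(1 − d), and the analysed cluster size, to 9(1 − d). At 10% loss, N is about 967, m = 8.1 and the equal-size VIF falls to 1 + 7.1 × 0.05 = 1.355. Power is 77.0%.

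| m = 9, 1075 enrolled | DE, GEE approx. | Power, GEE approx. | DE, size-weighted | Power, size-weighted |
|---|---|---|---|---|
| Equal sizes, no loss | 1.400 | 79.9% | 1.400 | 79.9% |
| CV 0.4, no loss | 1.451 | 78.5% | 1.472 | 77.9% |
| CV 0.6, no loss | 1.519 | 76.6% | 1.562 | 75.5% |
| CV 0.8, no loss | 1.627 | 73.8% | 1.688 | 72.2% |
| Equal sizes, 5% loss | 1.377 | 78.5% | 1.377 | 78.5% |
| Equal sizes, 10% loss | 1.355 | 77.0% | 1.355 | 77.0% |
| CV 0.6, 10% loss | 1.466 | 73.7% | 1.501 | 72.7% |

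**Step 4: dependence on m, still with 1075 patients.**
- 200 clusters: m = 1075 / 200 = 5.4, VIF = 1.22. Power is 85.1% with equal sizes, 82.3% (size-weighted) to 82.8% (GEE) at CV 0.6, and 79.3% to 79.8% at CV 0.6 with 10% loss.
- The 15-patient minimum in section 4.1: VIF = 1 + 14 × 0.05 = 1.70 and power is 71.9% with equal sizes and no loss. Table 3's own row for m = 15 asks for 768.32 × 1.70 = 1306 patients.

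**The case against.** Several points on the other side are sound.

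- **There is no arithmetic error.** The formula is standard, it is stated openly, and 1075 reproduces exactly. The issue is two assumptions that were left unmodelled.
- **The size-weighted factor does not match the planned analysis.** Exchangeable GEE gives large clusters less weight, so that factor overstates the shortfall, by up to about 1.6 points in the table. It serves only as a conservative bound.
- **The size of the effect is not in the documents.** The question about collaborative practice shows that practices differ, but gives no sizes. CV 0.4 alone or 5% loss alone costs only about 1.5 to 2 points.
- **Outcome loss may be low.** Section 3.9 speaks of missing data, not specifically of missing outcomes. There are no study visits, and events come from review of practice and hospital records (section 3.7.3).
- **A restated figure has limited reach.** It would still concern a difference in proportions, whereas the SAP treats the primary outcome as a number of events and reports a hazard ratio. A null result would in any case be read mainly from its confidence interval.

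A reader might go further and infer that the trial as a whole is underpowered. The documents do not support that. Sections 3.1 and 3.7.2 aim for 200 providers. If these formed 200 clusters, power would stay at 80% or more under each assumed CV up to 0.8 taken alone, and under 10% loss taken alone. That reassurance is itself uncertain: randomisation is by practice, so several providers in one practice would mean fewer and larger clusters.

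What remains after these objections is the lack of any margin at the plan's own m = 9, and the fact that the plan does not settle what m is.

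**Conclusion.** The point holds at the plan's own base case and is minor. With m = 9 and ICC 0.05, power is 79.9% only if all clusters are equal and every patient is analysed, and either departure lowers it. For CV 0.4 to 0.8 without loss the GEE approximation gives about 78.5% down to 73.8%. With 10% loss it gives 77.0% for equal sizes and 73.7% at CV 0.6. The direction follows from the design; the size rests on assumed CV and loss.

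The choice of m matters at least as much. The same 1075 patients give 85.1% at m = 5.4 and 71.9% at m = 15, both with equal sizes and no loss. No single power figure, 80% or lower, can be defended until the cluster unit and size are settled.

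**What to change.** Keep the sample size and amend section 3.8 in two respects.

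1. Restate the power from the actual number of randomised practices and the mean and CV of their sizes. Use a design effect that matches the exchangeable GEE, or the size-weighted factor labelled as conservative. Include any expected loss of outcome data, reducing the cluster size along with the total.
2. Reconcile the cluster unit and size: the ICC and m are per physician but randomisation is by practice; m is 9 in the base case, yet section 4.1 sets a minimum of 15 enrolled patients and a line in section 3.8 lists average sizes of 20, 25 and 30; Table 3 implies 119.5 clusters at the base case, against a goal of 200 providers.

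This needs no more patients and no change to the analysis. The cost is a short recalculation from enrolment data and, if the average cluster is near 9 or larger, a slightly less favourable stated power.
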